### **4.3. Exclusion Criteria**

General Exclusion Criteria for All Participants:

- Known allergies to oxytocin or to preservatives in the nasal spray

- Participants unable to tolerate the scanning procedures or would be unfit for scanning purposes (e.g. metal implants, claustrophobic, unable to lie still for the duration of the scan)
- Female subjects who are pregnant, trying to become pregnant, or nursing
- Any current or past history of any serious medical or neurological illness
- Acute or uncorrected medical illnesses, including history of hepatic or renal dysfunction, hyponatremia, traumatic brain injury, atrophic rhinitis, recurrent nose bleeds, and cranial-surgical procedures (hypophysectomy).
- Abnormal MRI (except if due to technical factors)
- Participants reporting use of an intranasal medication that could not be stopped 48 hours prior to each scanning session
- Participants taking medications including any current treatment with antipsychotics, antidepressants, mood stabilizers, psychostimulants and psychostimulant appetite suppressants, hormone use (i.e. testosterone, DHEA), opioid drugs, isoniazid, glucocorticoids, centrally active antihypertensive drugs (e.g., clonidine, reserpine), or sedative hypnotic medications (e.g. benzodiazepines, barbiturates, within 1 week prior to study enrollment).
- Unable to comply with study procedures or protocols

Additional Exclusion Criteria for Control group:

- Any reported current (within the last 2 months) use of any category of illicit drugs

Additional Exclusion Criteria for AUD group:

- History of, or current, psychotic disorder, antisocial personality disorder, or bipolar disorder
- Concurrent posttraumatic stress disorder
- Dependence (moderate to severe) to any other substance within the last 2 months other than alcohol or nicotine

Written informed consent will be obtained. Participants who exhibit nasal obstruction or upper-respiratory tract infection at the time of scanning, test positive on drug and/or ethanol screens, or are affected by a condition or abnormality that in the opinion of the Investigator would compromise the safety of the patient or the quality of the data will be withdrawn from the study. Additionally, female subjects of childbearing potential must agree to use effective methods of birth control discussed during the consenting process throughout the duration of the study in order to participate. Acceptable methods of birth control include hormonal birth control (e.g. birth control pills, skin patches, shots, under-the-skin implants, or vaginal ring), a barrier contraceptive such as a condom with spermicide cream or gel, diaphragms or cervical cap with spermicide cream or gel, an intrauterine device (IUD), tubal ligation or partner vasectomy, or avoiding sexual activity that could cause them to become pregnant. If a female subject indicates she suspects she is pregnant or tests positive on a pregnancy screen, she will be withdrawn from the study.

## 5. STUDY TREATMENTS

### 5.1. Allocation to Treatment

Eligible participants will be randomly assigned to administer either Syntocinon® or placebo first, prior to scanning using a computer-generated randomization scheme. Neither the research staff, nor the participants will know the identity of the test and control drugs. On behalf of PharmaWorld, Volkapotheke Roten Ochsен will transfer Syntocinon® into bottles identical to placebo using sterile procedures. To maintain the blind, packaging and labeling of test and control treatments will be identical to maintain the blind.

### 5.2. Breaking the Blind

The randomization can be broken, if necessary per the physicians caring for the subject (or at the request of the IRB) to ensure subject safety. With the exception of a medical emergency, the blind will only be broken by the PI.

[figure not shown]
### 5.3. Drug Supplies

Syntocinon® will be supplied by the international pharmacy, PharmaWorld, located in Zurich, Switzerland. Syntocinon® solution will be contained within 5mL bottles (contain a total of 40 IU of oxytocin). Volkapotheke Roten Ochsен will rebottle the Syntocinon® into bottles identical to those used for the placebo spray that will dispense Syntocinon® at a rate of 4 IU/0.1 mL/puff.

#### 5.3.1. Formulation, Preparation and Dispensing

Syntocinon® (oxytocin) is a synthetic, (1-6) cyclic nonapeptide. Chemically, oxytocin is designated as Glycinamide, L-cysteinyl-L-tyrosyl-L-isoleucyl-L-glutaminyL-L-asparaginyL-L-cysteinyl-L-prolyl- L-leucyl-, cyclic (1-6)-disulfide.

The structural formula is:

Syntocinon® (oxytocin) spray is provided as a sterile solution for intranasal administration. Each 5 mL of solution contains 40 USP or International Units of oxytocin and contains the following inactive ingredients: E 216, E 218 and chlorobutanol hemihydrate as preservatives, excipients to 1 mL.

#### Formulation of Control Product

A placebo solution (containing the same ingredients as the Syntocinon® spray minus oxytocin) will be placed into identical bottles by Volkapotheke Roten Ochsен and supplied by PharmaWorld.

### **5.3.2. Administration**

Participants will be asked to self-administer 3 puffs of placebo or Syntocinon® per nostril (for Syntocinon®, this corresponds to 4 IU/puff, for a total of 6 puffs/24 IU). Participants will administer placebo and Syntocinon® while seated, inhaling a full spray per nostril, alternating between nostrils, waiting 15 seconds between each puff (total of 6 puffs). Participants will be studied on two separate occasions, approximately 1-2 weeks apart in a double-blind design where the order of Syntocinon® and placebo is randomized across subjects.

### **5.3.3. Drug Storage and Drug Accountability**

#### **5.3.3.1. Supply of Study Drug at the Site**

Syntocinon® and placebo will be shipped by the international pharmacy, PharmaWorld, located in Zurich, Switzerland to the University of Utah. Drug shipment will occur once all the required regulatory documentation has been received and the study approved by the University of Utah Institutional Review Board.

#### **5.3.3.2. Storage**

Syntocinon® and placebo will be stored at limited access lab at the University of Utah in a refrigerator (2-8°C). If the temperature of the study drug storage exceeds or falls below this range, this will be reported and captured as a deviation.

#### **5.3.3.3. Study Drug Accountability**

Subjects will be asked to self-administer study drugs. An accurate and current accounting of the dispensing of study drug for each subject will be maintained on an ongoing basis by a member of the study site staff. The number of study drug dispensed and returned by the subject will be recorded on the Drug Accountability Record. The study monitor will verify these documents throughout the course of the study.

### **5.4. Concomitant medications**

Participants who utilize intranasally administered medications that cannot be stopped 48 hours prior to each scanning session will be excluded. Participants reporting current treatment with the following medications will be excluded: antipsychotics, antidepressants, mood stabilizers, psychostimulants and psychostimulant appetite suppressants, testosterone, DHEA, opioid drugs, or treatment with isoniazid, glucocorticoids, centrally active antihypertensive drugs (e.g., clonidine, reserpine), or sedative hypnotic medications (benzodiazepines, barbiturates) within 1 week prior to study enrollment.

## **6. STUDY PROCEDURES**

We will require written informed consent from all study participants prior to entering the study. A table of study activities is given in section 6.8.

### **6.1. Screening**

#### **6.1.1. Demographics**

Demographic information (date of birth, gender, ethnicity, race) along with handedness will be recorded at Screening.

#### **6.1.2. Medical History**

If the participant meets inclusion criteria, informed consent will be obtained. All relevant medical history, including history of current or past history of neurological or psychiatric illness, will be recorded. Current and past drug use (illicit and prescribed) will also be recorded. Participants will also be asked questions to determine whether they would be fit for fMRI scanning (e.g. if they are claustrophobic, unable to lie still for the duration of the scan, have metal implants). Participants will be asked whether they will be able to self-administer an intranasal medication (including whether they currently are experiencing nasal obstruction, upper-respiratory tract infection or utilize intranasally administered medications that could not be stopped 48 hours prior to each scan). Participants will also be specifically asked whether they have any known allergies to oxytocin or to preservatives used in the spray.

## **6.2. Intake**

1. If the participant has been determined to meet criteria for the study, we will review the study with the participant and obtain informed consent.
2. Participants will be asked to submit to a urine drug screen to ensure no current illicit drug use and asked to give a saliva sample for ethanol screening. Pregnancy tests will also be done on female participants.
3. Participants will undergo a psychiatric interview to verify that participants meet study criteria.
4. Participants will be asked to perform the American National Adult Reading Test (AMNART, v2).
5. Participants will be asked to complete questionnaires at intake to assess trait measures of mood, personality, drug and alcohol use, and attachment that are expected to take approximately 2 to 2.5 hours (see section 6.10).
6. Participants will undergo an effort based task (PR task) designed to assess motivation for monetary incentives.
  - The PR task has been previously described (Chelonis et al 2011). During this task, participants will be instructed to repeatedly press a key in front of them over 5 minutes. They will be informed that if they press the key enough times, they will receive a quarter, and if they continue to press the key they will continue to win quarters (up to \$5 dollars).
7. Ask participant to give a saliva sample for genetic testing (see section 6.3.3 regarding saliva analysis).
8. Schedule the participant for their scanning sessions and give them detailed information regarding their scanning day including location and schedule.

## **6.3. Scanning Day Measurements**

### **6.3.1. Drug, Alcohol, & Pregnancy Screen**

Urine will be collected and a drug screen, and if applicable, a pregnancy screen will be performed prior to each scanning session. A saliva ethanol test will also be done. Participants will be asked to refrain from alcohol use 24 hours prior to each visit.

[figure not shown]
### **6.3.2. fMRI Scanning**

Functional MR images will be acquired on a research dedicated 3 Tesla scanner (Philips) located at the University of Utah. Each of the fMRI tasks described below will be programmed using E-prime software and presented to subjects via a display placed behind the gantry. Subjects will enter the scanner approximately 30 minutes following drug administration so that scanning coincides with peak oxytocin levels [3,21,32,33].

### 6.3.2.1. fMRI Tasks

#### Modified Incentive Delay Tasks

The paradigm to be utilized has been used by our laboratory and others to assess functioning of the motivational circuitry in response to monetary rewards (i.e. Monetary Incentive Delay Task, MID) [34-36]. In this adapted paradigm, subjects will be presented with an incentive cue (shape) which signals the potential to either win money, avoid losing money, or whether no money is at stake (See Figure 1). Subjects can earn/avoid losing money during these conditions by pressing a button when a target box, presented after the incentive cue is on the screen. The reaction time used to define the presentation time for the target will be adjusted to ensure a ~66% success rate. Following the target box, subjects will see a feedback screen which will inform them whether they successfully won money or avoided losing money.

**Figure 1. Example of a Single Trial in the MID Task.** Adapted from Knutson, 2000.

**Figure 2. Example of social incentive feedback.** Stimuli taken from Rademacher, 2010.

During some of the trials (i.e. during the Social Incentive Delay Task, SID), the feedback screen will feature a social incentive (i.e. happy faces if they won or successfully avoided losing money or upset faces if they failed to win or lost money). Previous studies performed by Spreckelmeyer and colleagues (Figure 2) have demonstrated that the brain responds differently to social incentives compared to just monetary rewards [37,38]. During the social reward trials, participants will be told that they will be performing this task on behalf of another (a study member) who will be sitting outside of the scanner observing their performance. When the participant successfully 'wins' they will see a picture of that study member's smiling face and if they fail to avoid losing, they will see a picture of that study member's upset face.

Following the scan, the participant will be asked to provide VAS ratings to determine how they felt about the cues from the SID and MID and the feedback screens to examine their affective reactions.

#### Hemodynamic Response Function (HRF) Task

This paradigm is used to determine the Hemodynamic Response Function (HRF) which shows how a person's BOLD signal changes over time in response to changes in brain activity which corresponds approximately to changes in blood flow and corresponding oxygen consumption. This is a useful measure to collect to aid in the analysis of fMRI data and can be used to determine whether pharmacological agents have more generalized effects on BOLD activity. In this task, participants will be asked to look at either a fixation cross or a flashing

checkerboard. When the flashing checkerboard is onscreen, participants will be asked to press their thumbs and forefingers together rapidly.

### Why-How Task / Photography Judgment Test

This paradigm is used to explore the processing of social cues. Specifically, participants are asked to make judgments about each of the photos (i.e. Photography Judgment Test) by answering a series of yes or no questions paired with a set of photographs featuring facial expressions or intentional actions (Figure 4). This measure will help determine whether oxytocin can influence the basic processing of social information which may in turn interfere with responses to social rewards.

### Anatomical/Connectivity Scans

Anatomical scans will be acquired on the same 3 Tesla scanner used to collect the functional data. Two sets of anatomical images will be collected: high resolution anatomical scans and a lower resolution anatomical scan acquired in the same slice locations as the functional scans to improve standardization. Anatomical/Connectivity scans may include a high resolution T1-weighted image used for anatomical standardization to a standardized template, resting state, and diffusion tensor imaging to map white matter.

#### 6.3.2.2. Post Scanning Tasks

##### Delayed Discounting

We will use this brief task to examine the extent to which individuals discount delayed rewards. During the task, participants will be asked to respond to a series of hypothetical choices. In the first series of choices, participants will be asked to imagine a hypothetical scenario where they could receive money. They are then asked to decide between different amounts of money being delivered at various times. For example, would they prefer to receive "\$50 now" vs "\$100 in a month" or "\$50 now" vs "100 in a year". An algorithm will be used to determine the participants' individual discount rate. In the second series of choices, participants will be asked to make similar choices but to imagine that they could be sharing this reward with another person.

##### Time Perception

Related to the concept of delayed discounting is the ability to correctly perceive time. In order to test this, participants will be asked to click a button when they believe a certain amount of time has passed (e.g. 1 minute). Participants will be explicitly instructed not to count during their performance of the task.

[figure not shown]

Figure 3. Depiction of the Why/How Task. Image from Spunt, 2014.

## Facial Emotion Recognition Task (FERT)

This task will determine how well participants are able to recognize facial expressions of emotion. This particular ability has been previously demonstrated to be influenced by oxytocin administration. During this task, participants will be told that they will see a series of faces (see Figure 4) with various emotional expressions (e.g. happy, sad, fear, anger). Faces will be displayed on a computer screen and participants will be told to rate the intensity of the emotion the faces is displaying.

**Figure 4. Example of FERT Faces.** Stimuli taken from NimStim Face Stimulus Set

### 6.3.3. Saliva Collection

Saliva will be obtained at intake for those participants who allow genetic analyses to be performed on their saliva. These samples will be labeled with the participant's unique ID number and stored in a laboratory freezer until assayed. Saliva will later be processed and analyzed for genetic analyses. Saliva will be collected during the scanning sessions for future testing of hormone levels.

### 6.4. Scanning Session 1

1. Review procedure with participant, noting any changes in health (such as nasal congestion or upper-respiratory issues) prior to drug administration.
2. Collect urine and saliva for drug and ethanol screening to ensure no acute drug use. A urine pregnancy test will be done for female participants. Record blood pressure and heart rate. Ask participant to give a saliva sample for laboratory testing.
3. Participant will practice the fMRI tasks on a laptop to become acquainted with each of the tasks.
4. Participant will self-administer either placebo or Syntocinon® (blinded to both research staff and participant) over 5 minutes.
5. Record and respond to any adverse experiences. Record blood pressure and heart rate.
6. Ask participant to complete measures designed to assess mood, social perception and anxiety while waiting for scanning (see section 6.10).
7. Participant will be placed into the scanner and scanned under several conditions which may include:
  - a. Preliminary scans including collection of anatomical overlay
  - b. MID task
  - c. SID task
  - d. HRF task
  - e. Why/How / Photography Judgement Task
  - f. Anatomical / connectivity images
8. Ask participant to complete the delayed discounting and FERT.
9. Ask participant to rate faces (e.g. trustworthiness) that may have given as part of the

SID task. Record blood pressure and heart rate. Ask participant to give a saliva sample for laboratory testing.

10. Any adverse events will be recorded and information for the next scanning session will be provided. A phone number will be collected so the participant can be contacted the next day to follow-up on any potential effects.

### **6.5. Scanning Session 1 Follow-up**

1. Call participant and check on any adverse events that may have occurred following the scanning session.
2. Verify schedule for the next scanning session.

### **6.6. Scanning Session 2**

1. Review procedure with participant, noting any changes in health (such as nasal congestion or upper-respiratory issues) prior to drug administration.
2. Collect urine for drug screen and perform urine drug analysis to ensure no acute drug use. Record blood pressure and heart rate. Ask participant to give a saliva sample for laboratory testing.
3. Participant will practice the fMRI tasks on a laptop to remind them how to perform each of the tasks.
4. Participant will self-administer either placebo or Syntocinon® (blinded to both research staff and participant) over 5 minutes.
5. Record and respond to any adverse experiences. Record blood pressure and heart rate.
6. Ask participant to complete several measures designed to assess mood, social perception, and anxiety while waiting for scanning.
7. Participant will be placed into the scanner and scanned under several conditions which may include:
  - a. Preliminary scans including collection of anatomical overlay
  - b. SID task
  - c. MID task
  - d. Hemodynamic Response Function
  - e. Why/How / Photography Judgement Task
  - f. Anatomical/connectivity images
8. Ask participant to complete the delayed discounting, time perception, and FERT.
9. Ask participant to complete measures designed to assess mood, social perception and anxiety (see section 6.10)
10. Ask participant to rate faces (e.g. trustworthiness) that may have been given as part of the SID task. Record blood pressure and heart rate. Ask participant to give a saliva sample for laboratory testing.
11. Any adverse events will be recorded and information for the next scanning session will

be provided. Participants will be asked questions regarding their scanning experience and to guess whether they received oxytocin or placebo during each scan. A phone number will be collected so the participant can be contacted the next day to follow-up on any potential effects.

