## **3. STUDY DESIGN**

This is a double-blind, placebo-controlled, randomized study of the effects of Syntocinon® on brain activity elicited during the processing of reward. Each participant will be studied twice using fMRI; once self-administering Syntocinon® and once self-administering placebo intranasally approximately 30 minutes prior to being scanned. Participants will be randomly assigned to self-administer either Syntocinon® or placebo first. Scans will be performed on separate days approximately 1-2 weeks apart.

Participants will be evaluated thoroughly at screening for eligibility and will only be entered into the study if they meet all inclusion criteria and none of the exclusion criteria.

88 participants are planned to complete the study (44 controls, 44 AUD). Total duration of the study is expected to be 60 months.

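### The time perception task is listed for Session 2 only, so as written it gives no within-person oxytocin–placebo comparison; the post-scan mood round has the same gap

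*Protocol*

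**What the plan says.** The trial is a two-session crossover. Each participant is scanned twice, "once self-administering Syntocinon® and once self-administering placebo intranasally approximately 30 minutes prior to being scanned" (section 3), and the order is random: "Participants will be randomly assigned to self-administer either Syntocinon® or placebo first".

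Section 6.3.2.2, which sits under Scanning Day Measurements, describes three post-scan tasks: delayed discounting, time perception and FERT. For time perception, "participants will be asked to click a button when they believe a certain amount of time has passed". Nothing there ties the task to one session.

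The step lists then differ:

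- Session 1 (6.4, step 8): "Ask participant to complete the delayed discounting and FERT".
- Session 2 (6.6, step 8): "Ask participant to complete the delayed discounting, time perception, and FERT".

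Session 2 step 9 adds, after the scan, "Ask participant to complete measures designed to assess mood, social perception and anxiety (see section 6.10"). In Session 1 the step after the post-scan tasks is the face ratings, and no such round appears.

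Before the scan the two sessions agree. Session 1 step 6 reads "Ask participant to complete measures designed to assess mood, social perception and anxiety while waiting for scanning (see section 6.10"), and Session 2 step 6 reads "Ask participant to complete several measures designed to assess mood, social perception, and anxiety while waiting for scanning". Both steps follow dosing.

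The Schedule of Activities (6.10) marks scanning questionnaires for both sessions. It does not separate pre-scan from post-scan administration and has no row for the post-scan tasks.

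**The concern.** A crossover gains its precision by comparing each person with themselves. A measure taken in one session only is seen under one treatment per person, so that comparison cannot be formed. The step lists put time perception in this position, while the two tasks described beside it are collected in both sessions. The post-scan round of mood, social perception and anxiety measures is in the same position.

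At stake is the precision of any oxytocin–placebo comparison on these two items. An analysis plan cannot recover it, because a Session 1 value that was never collected cannot be supplied later.

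**Working it through.** **Side by side**

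| Item | Session 1 (6.4) | Session 2 (6.6) |
|---|---|---|
| Mood, social perception, anxiety: after dosing, before scan | step 6 | step 6 |
| Delayed discounting, FERT | step 8 | step 8 |
| Time perception | not listed | step 8 |
| Mood, social perception, anxiety: after scan | not listed | step 9 |

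The step lists are the only place where the last two items are assigned to a session.

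**Inputs.** Planned completers are 88, of whom 44 are controls and 44 have AUD (section 3). The protocol gives no between-session correlation ρ for these measures, so ρ is assumed over a range. An even split by order is also assumed. The protocol states no figure on this point, so there is none to reproduce.

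**Variance.** Let s² be the variance of one measurement and N the number of participants.

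- Measured in both sessions: variance of the drug difference = 2s²(1−ρ)/N. For N = 88 this is s²(1−ρ)/44.
- Measured in Session 2 only, N/2 per order group: variance = 2s²/(N/2) = 4s²/N. For N = 88 this is s²/22.
- Ratio = (4/N) ÷ (2(1−ρ)/N) = 2/(1−ρ).

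| Assumed ρ | 2/(1−ρ) |
|---|---|
| 0 | 2.0 |
| 0.3 | 2/0.7 = 2.9 |
| 0.5 | 2/0.5 = 4.0 |
| 0.7 | 2/0.3 = 6.7 |

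Even with no correlation between sessions the variance doubles, because half the measurements are missing.

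**Detectable difference, in units of s.** The only power statement in the protocol (8.1) uses a one-sided 0.005 threshold and 90% power, for brain regions and not for these tasks. It is borrowed here as a yardstick, with the noncentral t distribution:

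| | Session 2 only | Both, ρ = 0.3 | Both, ρ = 0.5 | Both, ρ = 0.7 |
|---|---|---|---|---|
| One diagnostic group (22 v 22, or 44 paired) | 1.21 | 0.72 | 0.61 | 0.47 |
| All participants (44 v 44, or 88 paired) | 0.84 | 0.50 | 0.42 | 0.33 |

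At the more usual two-sided 0.05 and 80% power, the all-participant figures are 0.60 for Session 2 only, against 0.36, 0.30 and 0.23 paired.

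**Time for the post-scan round.** Steps 6 and 9 refer to section 6.10, which is the schedule; the questionnaires are listed in 6.11. The protocol does not say which of them make up the post-scan round. If it is the whole scanning battery in 6.11, the listed times add up to 5 + 1 + 2 + 2 + 3 = 13 minutes at the low end and 5 + 2 + 5 + 3 + 3 = 18 minutes at the high end.

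**The case against.** The strongest reply is that this is a slip in a list and not a design decision. Section 6.3.2.2 reads naturally as covering every scanning day, and the step lists are incomplete elsewhere. The Session 2 list omits the ethanol and pregnancy tests, which 6.3.1 and 6.10 require at both sessions. The post-scan VAS ratings of cues and feedback in 6.3.2.1 are named in neither list. This stands: the text does not show that the sponsor chose to leave time perception out of Session 1. It does not remove the problem, because staff working from 6.4 would still omit the task.

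Three stronger readings are tempting, and the documents support none of them.

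- A reader might infer that the drug comparison on mood, social perception and anxiety is lost. It is not. Step 6 of each session measures these constructs after dosing, so a paired comparison exists. Only the post-scan round lacks one. A pre-to-post change within Session 2 does not supply it, since both values fall under the same treatment.
- A reader might infer that no valid drug comparison remains for time perception, or that the crossover is wasted. Order is randomized, so Session 2 still gives a randomized between-person contrast. It is less precise, and it relies on the Session 1 treatment leaving no trace in Session 2. Discounting, FERT, the pre-scan measures and the fMRI tasks stay paired.
- A reader might infer that time perception was included to interpret the discounting results, which would then suffer. The protocol says only that the two are related; it states no such purpose.

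It is also fair to say that neither item appears in an objective (2.1.1) or in a planned analysis (section 8). The detectable differences above therefore show lost precision, not harm to a stated aim.

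**Conclusion.** The point holds as a minor inconsistency with a real but limited cost. Section 6.3.2.2 and the Session 1 list in 6.4 do not agree with the Session 2 list in 6.6. Followed as written, time perception yields one value per person and only a between-person drug comparison. The variance is 2.9 to 6.7 times that of the paired contrast for ρ from 0.3 to 0.7, and twice at ρ = 0. These figures rest on an assumed ρ, equal variances in the two sessions and an even split by order. The same loss applies to the post-scan mood round, but not to the pre-scan measures of the same constructs. Both items are exploratory, and the primary fMRI objectives are untouched.

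**What to change.** 1. Add time perception to 6.4 step 8, so that it matches 6.6 step 8 and 6.3.2.2. The cost should be a few minutes per participant in Session 1; the protocol gives no duration for the task. If the omission is deliberate, state the reason.
2. Make the post-scan questionnaires the same in both sessions by adding a step to 6.4 that mirrors 6.6 step 9. This costs up to about 13–18 minutes if the round is the full scanning battery, and less if it is a subset. Alternatively, keep the round in Session 2 only and state that it is descriptive and not used for a drug comparison, which costs nothing. Either way, name the measures in the round and point to 6.11.
3. Add rows to the 6.10 schedule for the post-scan tasks and for the pre-scan and post-scan questionnaires, so that 6.3.2.2, 6.4, 6.6 and 6.10 agree.
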